7.4 Safety Monitoring Committee (SMC) Reviews

The SMC for this study will be comprised of an independent group of experts who review safety data during the clinical trial. The SMC will meet as needed to deliberate upon the disposition of study pauses and/or to provide other recommendations regarding the safe conduct of the study as requested by the PI and study team. Otherwise the SMC will review study data, at a minimum annually from the time the study opened. The SMC Executive Secretary will provide the PI and study team with SMC recommendations, and the PI and MHRP Consultants will inform IRBs and regulatory authorities as appropriate. The VRC will notify the FDA of the SMC recommendation as needed.

7.5 Criteria for Study Pause or Termination

The PI will closely monitor and analyze study data as they become available and will make determinations regarding the presence and severity of adverse events. The administration of study injections and new enrollments will be paused and the IND Sponsor will be promptly notified according to the following criteria:

- **One** (or more) participant experiences a **SAE** that is assessed as possibly, probably or definitely related to study agent, or
- **Two** (or more) participants experience the same **Grade 3 or 4** adverse event assessed as possibly, probably or definitely related to study agent.

Plan for Review of Pauses and Resuming Rules:

The study injections and enrollments would resume only if review of the adverse events that caused the pause resulted in a recommendation to permit further study injections and study enrollments. The reviews to make this decision will occur as follows:

Pauses for SAEs: The IND Sponsor and PSRT will consult with the SMC to conduct the review and make the decision to resume, amend or close the study for any SAEs that meet the criteria for pausing the study. The FDA will be notified of any SAE pause review.

Pauses for Grade 3 or 4 AEs: The IND Sponsor and PSRT will conduct the review and make the decision to consult the SMC, resume, amend or close the study for the Grade 3 or 4 events that meet the criteria for pausing the study. As part of the pause review, the reviewers will also advise on whether the study needs to be paused again for any subsequent Grade 3 or 4 event of the same type. The FDA will be notified of all Grade 3 or 4 pause reviews.

When indicated, safety data reports and changes in study status (study pauses) will be submitted to the IRB in accordance with institutional policy.

7.6 Reporting Serious and Unexpected Adverse Events

7.6.1 Study Reporting Period for SAEs

The protocol-defined expedited event reporting period is 48 weeks after study agent administration (study completion) or discontinuation of the participant from study participation for any reason. After the end of the protocol-defined SAE Reporting Period stated above, sites must report suspected unexpected serious adverse reactions (SUSARs) if the study site staff becomes aware of the event from a participant on a passive basis (i.e., from publicly available information).

7.6.2 Adverse Event Reporting to the IND Sponsor

All SAEs must be reported and submitted by the clinical site on an expedited basis to the IND sponsor, VRC/NIAID/NIH, according to sponsor guidelines as follows:

- results in death
- is life threatening
- results in persistent or significant disability/incapacity
- requires unplanned inpatient hospitalization or prolongation of existing hospitalization
- is a congenital anomaly/birth defect in the offspring of a study participant
- is an important medical event that may jeopardize the participant or may require intervention to prevent one of the other outcomes listed above

In addition, any event, regardless of severity, which in the judgment of an investigator represents a serious adverse event, may be reported on an expedited basis.

An investigator will communicate the initial SAE report within 24 hours of site awareness of occurrence to the IND sponsor throughout the study reporting time period. Notification of SAEs will be sent via email to the PSRT, which includes the IND Medical Officer.

A written report by investigator should be submitted to the IND Sponsor within 3 working days. In order for the IND Sponsor to comply with regulations mandating sponsor notification of specified SAEs to the FDA within 7 calendar days, the investigator must submit additional information as soon as it is available.

7.6.3 IND Sponsor Reporting to the FDA

The IND Sponsor is responsible for making the determination of which SAEs are SUSARs that meet criteria for expedited reporting as defined in 21 CFR 312.32.

- *Suspected adverse reaction* means any adverse event for which there is a reasonable possibility that the drug caused the adverse event.
- *Unexpected Adverse Event* means an AE that is not listed in the Investigator's Brochure or is not listed at the specificity or severity that has been observed.

The IND Sponsor will submit written IND Safety Reports to the FDA in accordance with 21 CFR 312.32 as soon as possible and, in no event, later than 15 calendar days after determining that the information qualifies for reporting.

The IND Sponsor is responsible for providing copies of IND Safety Reports for submission to the MUSPH IRB, UNCST and NDA as applicable.

7.6.4 Reporting Serious and Unexpected Adverse Events to the Local Regulatory Bodies & Institutional Review Boards

All SAEs regardless of relationship to the intervention and all unexpected events (whose nature, severity or frequency had not been identified in the Investigator's Brochure or the protocol) of greater than moderate severity regardless of relationship to the intervention, to include SUSAR, must be reported to the MUSPH IRB and the NDA as soon as possible and in any case no later than 7 calendar days of becoming aware of the event. Thereafter, a detailed report of the SAE should be submitted within 7 days.

All other reportable adverse events should be reported to the IRB as soon as possible and in any case no later than 14 calendar days. These include:

- a. All events associated with protocol violations regardless of severity and relationship to the intervention;
- b. When the criteria for stopping or pausing a study as stipulated in the protocol is met;
- c. Any event mandated by regulatory authorities;
- d. Any event stipulated in the protocol as reportable to the regulatory bodies.

Follow up reports will be submitted as additional information becomes available. A summary of the non-serious adverse events and SAEs (both related and unrelated) that occurred during the reporting period will be included in the continuing review report (CRR) to the MUSPH IRB.

7.6.5 Reporting Serious and Unexpected Adverse Events to WRAIR and HRPO

All SAEs that are considered related or possibly related, and all deaths, will be promptly (within 48 hours) reported to the WRAIR HSPB. Written reports will be submitted within 10 working days to the WRAIR HSPB. The WRAIR HSPB will report SAEs to USAMRDC ORP HRPO as per SOP UWZ-C-636. Follow up reports will be submitted as additional information becomes available.

The WRAIR HSPB will be immediately notified if any study pause criteria are met. WRAIR HSPB will forward to USAMRDC ORP HRPO as per SOP UWZ-C-636.

7.7 Unanticipated Problems Reporting

All non-serious unanticipated problems (events not involving risk to participants or others) will be reported in the continuing review report to the MUSPH IRB.

All serious unanticipated problems involving risk to subjects or others (UPIRTSOs) (including but not limited to disclosure of personal health information, breach of confidentiality, destruction or loss of study records, unaccounted for study drug, etc.) should be promptly (within 48 hours) reported to the WRAIR HSPB and the IND sponsor via email. The PI will then forward a written report within 10 working days to the WRAIR HSPB.

All unanticipated events of greater than moderate severity, regardless of relationship to the intervention, will be reported to the MUSPH IRB as soon as possible and in any case no later than 7 calendar days of becoming aware of the event. A detailed report of the unanticipated event should be submitted within 7 calendar days from the date it is reported to the MUSPH IRB.

Follow up reports should be submitted as soon as additional information becomes available. A summary of the serious unanticipated problems will also be included in the continuing review report submitted to the MUSPH IRB and NDA.

Unanticipated problems related to the investigational product, such as problems with the actual product itself (e.g. visible discoloration or particulate matter not consistent with product description), will be promptly reported to the study sponsor (for reporting to the US FDA), MUSPH IRB and NDA by the PI.

The DoD medical monitor should also review all unanticipated events involving risk to participants or others and provide an independent assessment for submission to VRC/NIAID, WRAIR HSPB, MUSPH IRB, and NDA (as applicable). The WRAIR HSPB will report serious unanticipated problems, follow up reports and DoD medical monitor reports to the USAMRDC ORP HRPO as per UWZ-C-636.

8.0 STATISTICAL CONSIDERATIONS

8.1 Overview

The primary objective of this study is to assess the safety and tolerability of cAd3-EBO S at two dose levels. The secondary objective is to evaluate the antibody and Ebola Sudan GP-specific T-cell responses to the GP insert and cAd3 vector at 4 weeks after vaccination. An exploratory evaluation of immunogenicity, including assays with samples collected at different study timepoints, profiling vaccine-induced mRNA expression, and isolating MAbs to determine epitope specificity, will also be performed. A total of 40 participants will be enrolled with 20 to receive a 1×10^{10} PU/mL dose and 20 to receive a 1×10^{11} PU/mL dose of the cAD3-EBO S and followed up through 48 weeks post -vaccination.

8.2 Sample Size and Accrual

8.2.1 Power and Sample Size Calculations for Safety

The goal of the safety evaluation for this study is to identify safety concerns associated with vaccination. Occurrence of solicited local and systemic reactogenicity symptoms, occurrence of adverse and serious adverse events will be assessed as the proportion of participants experiencing such safety event. Table 4 below shows 95% confidence intervals for 0, 1, 2, 5, and 10 participants with observed events in each group or among all study participants.

Table 4. Exact 95% Confidence Intervals for the Proportion of Participants Experiencing a Safety Event

Group	Sample Size	Number of Participants with an Event(s) Observed				
		0	1	2	5	10
Each Individual Study Group	20	0% (0%-16.8%)	5% (0.1%-24.9%)	10% (1.2%-31.7%)	25% (8.6%-49.1%)	50% (27.2%-72.8%)
All participants	40	0% (0%-8.8%)	2.5% (0.06%-13.2%)	5% (0.6%-16.9%)	12.5% (4.2%-26.8%)	25% (12.7%-41.2%)

If no participants experience an event, the upper limit of a two-sided exact 95% CI would be 16.8% for an individual group and 8.8% for the entire study group. While this study is not necessarily powered to detect differences between groups, we would have 82% power to detect a difference of 40% ($p_1=0.1$ and $p_2=0.50$) using Barnard's exact unconditional test at a 5% two-sided level of significance.

Changes in laboratory measures from baseline will also be described. For continuous safety measures, Table 5 below shows minimum detectable changes from baseline to a specified time point using a paired t-test with a two-sided 5% level test.

Table 5 Minimum Detectable Differences, in Standard Deviations, for Change From Baseline to a Single Time (2-sided $\alpha=0.05$)

Group	Sample Sizes	Power		
		80%	85%	90%
1 (1×10^{10} PU/mL)	15	0.78	0.83	0.9
2 (1×10^{11} PU/mL)	20	0.66	0.71	0.76
All Active	35	0.49	0.52	0.56

If comparing the two study groups, we would have 80% power to detect a difference of 0.91 standard deviations using a two-sample t-test with a two-sided 5% alpha and assuming equal variances.

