It is anticipated that about 100 volunteers will be screened in order to enroll a total of 40 participants. The 40 participants will be evenly split, with 20 in each of the two dosage groups for cAd3-EBO S. The dose escalation plan includes daily review of any new safety data by a study clinician, regular review of safety data by the protocol team and a staged enrollment plan with required interim safety reviews. The study will begin with enrollment of 3 participants into Group 1 at a rate of 1 participant per day. After at least 7 days of follow-up for the first 3 vaccinated participants, an interim safety review will occur before enrollment of additional participants into the group. If no safety issues are identified, an additional 17 participants will be enrolled to complete Group 1. When there is a minimum of seven days of follow-up safety data from the last enrolled participant in Group 1, an interim safety review will occur. Once no safety issues are identified, enrollment of participants into the next dose level (Group 2) will begin with the enrollment of 3 participants at a rate of 1 participant per day. After at least 7 days of follow-up for the first 3 vaccinated participants in Group 2, an interim safety review will occur before the enrollment of additional participants into Group 2. If no safety issues are identified, an additional 17 participants will be enrolled to complete Group 2.

Product Description

VRC-EBOADC086-00-VP (cAd3-EBO S) is composed of a cAd3 vector that expresses Ebola Sudan WT GP. It is formulated at 1×10^{11} PU/mL.

VRC-DILADC065-00-VP (diluent) is the formulation buffer used for vaccine production and will be used when needed to prepare the 1×10^{10} PU/mL dose of cAd3-EBO S.

Participants

Healthy adults in the Kampala area aged 18-50 years will be enrolled.

Study Duration

Participants will be evaluated at 9 clinic visits over 48 weeks.

Study Objectives

Primary Objectives

- To evaluate the safety and tolerability of VRC-EBOADC086-00-VP when administered IM at a dose of 1×10^{10} particle units (PU) to healthy adults;
- To evaluate the safety and tolerability of VRC-EBOADC086-00-VP when administered IM at a dose of 1×10^{11} PU to healthy adults.

Secondary Objectives

- To evaluate the antibody response to the GP insert and cAd3 vector in VRC-EBOADC086-00-VP at 4 weeks after vaccination as assessed by GP ELISA and vector-specific neutralization assays, respectively.

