4.0 STUDY DESIGN AND POPULATION

This is a Phase I open-label, dose-escalation clinical trial to evaluate the safety, tolerability and immunogenicity of a recombinant vector for the Sudan strain of the Ebola virus. This study will be conducted at the MUWRP in Kampala, Uganda.

A total of 40 healthy adults, 20 in each dosage group, will receive a single vaccine injection of cAd3-EBO S at 1×10^{11} PU/mL or 1×10^{10} PU/mL. The study will begin with enrollment of 3 participants into Group 1. After at least 7 days of follow-up for the first 3 vaccinated participants, an interim safety review will occur before enrollment of additional participants into the group. If no safety issues are identified, an additional 17 participants will be enrolled to complete Group 1. When there is a minimum of seven days of follow-up safety data from the last enrolled participant in Group 1, an interim safety review will occur. Once no safety issues are identified, enrollment of participants into the next dose level will begin with the enrollment of 3 participants. After at least 7 days of follow-up for the first 3 vaccinated participants in Group 2, an interim safety review will occur before enrollment of additional participants into Group 2. If no safety issues are identified, an additional 17 participants will be enrolled to complete Group 2. For the first 3 participants in each group, only one participant per day will be enrolled. The study groups and vaccination schema is shown in Table 1.

Study agent administration will be on Day 0. The study includes daily review of any new safety data by a study clinician and weekly review of safety data by the Protocol Safety Review Team (PSRT). The staged enrollment plan and plan for interim safety reviews (Section 7.3) applies to both Group 1 and Group 2. The interim safety reviews will be conducted by the PSRT.

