8.3 Statistical Analysis

All analyses will be described overall and by vaccination group (Group 1 and Group 2). The safety and immunogenicity analysis will include all vaccinated participants. All statistical analyses will be performed using Statistical Analysis System (SAS), R, or S-Plus statistical software. No formal multiple comparison adjustments will be employed for safety endpoints or secondary endpoints.

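### Table 5 is calculated for 15 participants in Group 1 and 35 in total, but the trial enrols 20 and 40, so six of its nine minimum detectable differences are wrong for the planned design.

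*Combined protocol and SAP*

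**What the plan says.** The planned size is the same wherever the design is described. The schema says "The 40 participants will be evenly split, with 20 in each of the two dosage groups for cAd3-EBO S", Section 4.0 says "A total of 40 healthy adults, 20 in each dosage group", and Section 8.1 begins its enrolment statement with "A total of 40 participants will be enrolled with 20 to receive a". Table 1 and Section 6.1 agree. So does Table 4, in the same section as Table 5, which gives exact confidence intervals for 20 and 40 participants.

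Table 5 differs. For 80%, 85% and 90% power, with a paired t-test at the two-sided 5% level, its sample size and detectable differences in SD are:

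- Group 1: "15 0.78 0.83 0.9"
- Group 2: "20 0.66 0.71 0.76"
- Pooled: "All Active 35 0.49 0.52 0.56"

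The sentence directly below the table turns to the comparison between groups: "If comparing the two study groups, we would have 80% power to detect a difference of 0.91 standard deviations using a two-sample t-test". Section 8.2.2 then applies Tables 4 and 5 to the immunogenicity results. Section 8.3 defines the analysis set: "The safety and immunogenicity analysis will include all vaccinated participants".

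**The concern.** Section 8.2.1 appears to use two different sizes for Group 1: 15 in Table 5, and 20 in Table 4 and in the between-group calculations. Nothing in the documents accounts for 15. A dropout allowance would have to be 5/20 = 25% in Group 1 and zero in Group 2, and no expected loss is stated for either group.

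Table 5 is the only statement of sensitivity for change from baseline in the safety laboratory measures, which is one of the primary endpoints. Through Section 8.2.2 it also covers continuous immunogenicity results, for which Section 8.3.3 does plan one-sample t-tests of change. As printed, it tells the reader that the lower-dose group can detect 0.78 SD and the higher-dose group 0.66 SD at 80% power, although the groups are the same size. It also leaves unclear how many Group 1 participants are meant to contribute data.

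**Working it through.** **Inputs.** Planned n is 20 per group and 40 in total (schema, Sections 4.0, 6.1 and 8.1, Tables 1 and 4). Table 5 n is 15, 20 and 35. The test is a two-sided paired t-test with α = 0.05, at 80%, 85% and 90% power (Section 8.2.1).

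**Formula.** For a standardised change d, the paired t statistic follows a noncentral t distribution with n − 1 degrees of freedom and noncentrality d√n. With t* the 97.5th percentile of the central t on n − 1 degrees of freedom,

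power(d, n) = P(T > t*) + P(T < −t*),

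and the minimum detectable difference is the d at which this equals the target power.

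**Step 1: reproduce the printed table at its own n.**

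| n | t* | 80% | 85% | 90% | Printed |
|---|---|---|---|---|---|
| 15 | 2.145 | 0.7780 | 0.8324 | 0.9009 | 0.78 / 0.83 / 0.90 |
| 20 | 2.093 | 0.6604 | 0.7065 | 0.7645 | 0.66 / 0.71 / 0.76 |
| 35 | 2.032 | 0.4875 | 0.5214 | 0.5641 | 0.49 / 0.52 / 0.56 |

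All nine cells agree to two decimals. The Group 1 and pooled values were therefore computed with 15 and 35; these are not typing slips confined to the sample-size column. Two alternatives do not fit. For n = 15 the normal approximation gives 0.723 / 0.774 / 0.837, and a one-sided t-test gives 0.676 / 0.729 / 0.795.

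**Step 2: recalculate at the planned n.**

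| Row | n | 80% | 85% | 90% | Printed minus correct (rounded values) |
|---|---|---|---|---|---|
| Group 1 | 20 | 0.66 | 0.71 | 0.76 | 0.12 / 0.12 / 0.14 |
| Group 2 | 20 | 0.66 | 0.71 | 0.76 | 0 / 0 / 0 |
| All | 40 | 0.45 | 0.49 | 0.53 | 0.04 / 0.03 / 0.03 |

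The unrounded values for n = 40 are 0.4543, 0.4859 and 0.5256.

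**Step 3: power at the printed differences with the planned n.** Group 1 (n = 20) has 91.1%, 94.1% and 96.8% power at 0.78, 0.83 and 0.90 SD. All participants (n = 40) have 85.6%, 89.4% and 93.2% power at 0.49, 0.52 and 0.56 SD. The column labels say 80%, 85% and 90%.

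**Step 4: check which Group 1 size the rest of the section uses.** For the two-sample t-test the noncentrality is d/√(1/n₁ + 1/n₂), with n₁ + n₂ − 2 degrees of freedom.

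- 20 and 20: √(1/20 + 1/20) = 0.3162. The difference at 80% power is 0.909 SD, which matches the stated 0.91.
- 15 and 20: √(1/15 + 1/20) = 0.3416. The difference at 80% power is 0.986 SD, and power at 0.91 SD is only 73%.

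Barnard's test for 10% against 50%, by full enumeration, gives 82.2% power with 20 and 20 (stated 82%). With 15 and 20 it gives 71.9% if the smaller group has the lower rate and 80.6% if it has the higher rate. The between-group figures therefore fit 20 per group and do not fit 15 and 20.

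**The case against.** The strongest reply is that nothing in the trial depends on Table 5. The sample size is not derived from it. The safety case rests on the confidence intervals in Table 4, which use the correct sizes. Laboratory changes are to be described rather than tested, and power for group differences is disclaimed. Dose escalation and pausing rest on safety review and event counts. The error is also conservative, so no reader is led to think the trial more sensitive than it is, and each cell is right for the n printed beside it. All of this stands. It bears on how serious the error is, not on whether the table is wrong.

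Two further points also stand. First, the 0.91 SD figure does not by itself prove exactly 20 per group: 19 and 21 gives 0.910 and 18 and 22 gives 0.914, which also round to 0.91. What it shows is that 15 and 20 is incompatible. Second, 20 and 40 assume complete paired data. Section 5.5.1 bars replacement after injection, Section 5.6 stops research blood draws during pregnancy, and Section 8.3.3 anticipates missing responses. For immunogenicity, the corrected values are therefore a best case.

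An unstated evaluable-number assumption cannot be excluded as the origin of the 15. It would still have to be written down and applied to Group 2, the total and the 0.91 SD figure, which the section does not do.

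**Conclusion.** Table 5 is wrong as written for the planned design. The three Group 1 cells overstate the detectable difference by 0.12 to 0.14 SD, and the three pooled cells by 0.03 to 0.04 SD. The Group 2 row is correct. The difference the table shows between the two dose groups, 0.78 against 0.66 SD at 80% power, is not real.

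The consequence is modest. The error understates sensitivity, the trial has no powered primary hypothesis, and no enrolment, escalation, pause or analysis rule changes. It is a definite correction to the sample-size section rather than a threat to the trial.

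The conclusion assumes 20 vaccinated participants per group, each with a baseline and a follow-up value, and the paired t-test named in the plan.

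**What to change.** In Table 5, set Group 1 to n = 20 with 0.66, 0.71 and 0.76 SD, and the pooled row to n = 40 with 0.45, 0.49 and 0.53 SD. Leave the Group 2 row and the 0.91 SD sentence as they are. A short note that these values assume complete paired data would help, particularly for the immunogenicity use in Section 8.2.2.

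If 15 was intended as an evaluable number, state the assumption and its reason, apply it to both groups, and recalculate Group 2, the total and the between-group figures on the same basis.

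The cost is two sample sizes and six values in one table, with no change to the design or the analysis.
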